8.3.5 Cardiovascular and Death Events

Not applicable.

8.3.6 Disease-Related Events and/or Disease-Related Outcomes Not Qualifying as AEs or SAEs

Not applicable.

Asymptomatic elevations in amylase or lipase or both in participants treated with evobrutinib have been observed at a variety of time points and reported as TEAEs or noted as laboratory abnormalities. In RMS Study MS200527_0086, the incidence of TEAEs of lipase increased was slightly higher in evobrutinib 75 mg once daily and 75 mg twice daily arms (5 [9.4%] and 5 [9.3%], respectively) when compared to other arms (approximately between 4% to 6%). However, shifts from Baseline to highest grade on treatment were similar across all treatment arms for both amylase and lipase. In evobrutinib studies in other indications and in healthy participants, the incidence of TEAEs of increased amylase or lipase, or both was infrequent and no clinically meaningful differences were observed across treatment arms. Any elevation of $> 2 \times$ ULN of lipase or amylase and any type of pancreatitis are classified as AESIs.

- Liver related events

The elevations of transaminases observed in participants treated with evobrutinib were frequent, asymptomatic, and reversible on discontinuation of evobrutinib. The mechanism is unknown.

Evobrutinib liver AESIs will include transaminases ($> 3 \times \text{ULN}$), bilirubin elevations ($> 1.5 \times \text{ULN}$), biological Hy's Law cases based on laboratory data, any type of acute or chronic hepatitis (any grade), suspected drug-induced liver injury, acute or chronic hepatic failure, fibrosis, cirrhosis, and other liver damage-related conditions.

[figure not shown]
[figure not shown]
AESIs have to be reported immediately. For reporting of AESIs, see [Appendix 4](#).

8.4 Pharmacokinetics

- The following PK parameters will be calculated, when appropriate for evobrutinib and its metabolite MSC2729909A on Day 1 and Day 19:

Symbol	Definition
$\text{AUC}_{0-\infty}$	The AUC from time zero (= dosing time) up to infinity with extrapolation of the terminal phase.
$\text{AUC}_{0-t_{\text{last}}}$	The AUC from time zero (= dosing time) to the time of the last quantifiable concentration (t_{last}).
C_{max}	Maximum observed concentration.
t_{max}	The time to reach the C_{max} in a dosing interval.
$t_{1/2}$	The terminal half-life.
t_{lag}	The time prior to the first concentration at or above LOQ
CL/F	The apparent total body clearance following extravascular administration.
V_z/F	The apparent volume of distribution during the terminal phase following extravascular administration.
$\text{M/P}(\text{AUC}_{0-\infty})$	Molecular weight-corrected ratio of metabolite $\text{AUC}_{0-\infty}$ to parent $\text{AUC}_{0-\infty}$.
$\text{M/P}(C_{\text{max}})$	Molecular weight-corrected ratio of metabolite C_{max} to parent C_{max} .

CCI

C
C
I

- Whole blood samples of approximately 2 mL for measurement of plasma concentrations of evobrutinib and its metabolite MSC2729909A will be collected. Collection times are specified in the Schedule of Assessments (Section 1.3). The actual date and time (24-hour clock time) of each sample will be recorded to calculate actual time elapsed since the prior dose administration.
- The quantification of evobrutinib and its metabolite MSC2729909A in plasma samples will be performed using fully validated assay methods. Evobrutinib and metabolite concentrations will be used to evaluate the PK parameters of evobrutinib and its major metabolite.

C
C
I

[figure not shown]
- Remaining samples collected for analyses of evobrutinib and carbamazepine concentrations may also be used to evaluate safety or efficacy aspects related to concerns arising during or after the study. Additionally, remaining plasma samples may be used for investigation of other evobrutinib metabolites, if deemed necessary.
- Details on processes for collection and handling of these samples are in the Laboratory Manual. Retention time and possible analyses of samples after the End of Study are specified in the respective ICF.
- PK parameters will be derived using noncompartmental methods with the validated computer program Phoenix® WinNonlin® (version 6.4 or higher).

The exact date and time of sample collection and study intervention administration prior to sample collection (24-hour clock time) must be recorded in the eCRF and will be used in the calculation of PK parameters. The accepted time deviations from planned evobrutinib and carbamazepine PK times that will not be considered a protocol violation are listed below:

Procedure	Time Point (Relative Time)	Window Allowance
Pharmacokinetics	Predose	- 60 min
	0.25 to 1 hours postdose	- 2 / + 2 min
	> 1 to 12 hours postdose	- 5 / + 5 min
	> 12 to 24 hours postdose	- 15 / + 15 min

Any deviation from the above-mentioned time windows requires a comment in the eCRF and may be discussed in the data review meeting.

CCI

CCI

9

Statistical Considerations

[figure not shown]
All planned analyses defined in this protocol will be described in the IAP that will be finalized before the database lock.

Changes in the conduct of the study or planned analyses, if any, will be reported in the appropriate section of the IAP and in the clinical study report.

[figure not shown]
9.1 Statistical Hypotheses

The statistical analysis of study data will be purely descriptive; no hypothesis tests will be performed. A definition of primary, secondary, and CCI and endpoints can be found in Section 3.

CCI

CCI

9.3 Analyses Sets

The analysis sets are specified below.

Analysis Set	Description
SCR	All participants, who provided informed consent, regardless of the participant's enrollment and study intervention status in the study.
SAF	All participants, who were administered any dose of any study intervention. Analyses will consider participants as treated.
PK	The PK Analysis Set is a subset of the SAF, and the PK population will include all participants: Who have completed the study without any relevant protocol deviations and factors likely to affect the comparability of PK results. With adequate study intervention compliance. With evaluable PK data, i.e., nonmissing values for primary endpoints. If participants received prohibited concomitant therapy or medicines, as specified in Section 6.8, they will be excluded from the PK population. All PK analyses will be based on this analysis set.

PK=pharmacokinetics; SAF=safety; SCR=Screening.

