1.2 Schema

1.3 Schedule of Activities

Assessments & Procedures	Screening													Safety Follow-Up	Notes	
Study Day	-28 to -2	-1	1	2	3	4	5	6 to 17	18	19	20	21	22	23 to 25	26	
Informed consent	X														Prior to any screening activity.	
Participants resident at CRU		X	X	X	X	X	X		X	X	X	X			X	
Eligibility criteria	X	X														Recheck of eligibility criteria on Day -1, (Sections 5.1 and 5.2).
Demography, height & weight	X															Demography to include, at minimum age (year of birth), sex, race, and ethnicity.
Medical history	X															
Physical examination	X	X													X	Brief examination on Day -1 Section 8.2.1.
FSH	X															In postmenopausal women.
Viral serology, TSH, QuantiFERON® test	X															
Clinical laboratory tests (blood and urine)	X	X						X ^a	X						X	a Safety lab to be collected from Day 10 to Day 14. Appendix 5 and Section 8.2.4.
Cotinine, drug screen, alcohol breath test, SARS-CoV-2	X	X														Appendix 5.
Safety ECG & vital signs	X	X	X	X					X	X	X				X	Predose, 4 and 6 hours postdose on Days 1 and 19. Sections 8.2.2 and 8.2.3.
AE/concomitant medication review	X	X	X	X	X	X	X	X	X	X	X	X	X	X		Section 6.8.
CCI																

Assessments & Procedures	Screening														Safety Follow-Up	Notes
Study Day	-28 to -2	-1	1	2	3	4	5	6 to 17	18	19	20	21	22	23 to 25	26	
Carbamazepine administration, mg				2x 100	2x 100	2x 200	2x 200	2x 300	2x 300	2x 300	2x 200 ^b	2x 200 ^b	2x 200 ^b	2x 100 ^b		First dosing on Day 2 after 24-hour PK sampling for evobrutinib. ^b On Day 20 evening dose, as well as on Days 21 to 25, participants will take carbamazepine at home. Twice daily administration (2x). Section 5.3.1, Section 6.1.
CCI									C C I	C C I					C C I	
Evobrutinib administration			X							X						Section 5.3.1, Section 6.1.
Evobrutinib and metabolite PK blood sampling			X	X						X	X					Sampling Days 1/2 and 19/20: Predose and 0.25, 0.5, 1, 1.5, 2, 2.5, 3, 4, 6, 8, 12, 16 and 24 hours postdose. Section 8.4.

CRU=clinical research unit; ECG=electrocardiogram; FSH=follicle stimulating hormone; PK=pharmacokinetics; SARS-CoV-2=severe acute respiratory syndrome coronavirus 2; TSH=thyroid stimulating hormone.

2 Introduction

Evobrutinib is an oral, selective, irreversible inhibitor of BTK which is in clinical development for the treatment of autoimmune diseases, including RMS.

Detailed information on the chemistry, pharmacology, efficacy, and safety of evobrutinib is in the IB.

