4.4 End of Study Definition

The end of the study is defined as the date of last contact (related to this study) with the last participant who participates in this study (last participant's Safety Follow-Up assessment).

A participant has completed the study if he/she has completed all study parts, including the Safety Follow-Up assessment shown in Section [1.3](#).

Study Termination Criteria

The study will be discontinued or terminated if:

- unacceptable risk, any relevant toxicity, or a negative change in the risk/benefit assessment is identified. This might include the occurrence of AEs which character, severity or frequency is new in comparison to the existing risk profile.
- any data derived from other clinical trials or toxicological studies become available which negatively influence the risk/benefit assessment.

General information on study termination are specified in [Appendix 2](#).

5 Study Population

The criteria in Sections [5.1](#) and [5.2](#) are designed to enroll only participants, who are appropriate for the study; thereby, ensuring the study fulfills its objectives. All relevant medical and nonmedical conditions are considered when deciding whether a participant is suitable for this study.

Prospective approval of protocol deviations to inclusion and exclusion criteria, also known as protocol waivers or exemptions, is not permitted.

Before performing any study assessments that are not part of the participant's routine medical care, the Investigator will confirm that the participant has provided written informed consent, as indicated in [Appendix 2](#).

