6.8.3 Prohibited Medicines

Prohibited medicines at study entry are indicated in the exclusion criteria (Section [5.2](#)).

The participants are prohibited from using prescription or over-the-counter medications (apart from those described above) within 2 weeks or 5 terminal half-lives, whichever is longer, prior to the first administration of study intervention, during the study, and until the Safety Follow-Up assessment (this includes herbal remedies, vitamins, minerals, antacids and dietary supplements such as fish oils).

Inhibitors or inducers of CYP3A4/5 ([Appendix 7](#)) or P-gp within 4 weeks prior to the first administration of study intervention, and until after the Safety Follow-Up assessment are prohibited. Also, drugs mainly metabolized by CYP3A4/5 and that have a narrow therapeutic index should be avoided.

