10.2 Protocol Deviations / Exclusion from Analysis Sets

10.2.1 Important Protocol Deviations

Listings of important protocol deviations will be provided including the date and relative day in relation to dosing in the relevant period. A distinction will be made between important protocol deviations due to COVID-19 versus not due to COVID-19. The respective important protocol deviations will be flagged accordingly.

Important protocol deviations or important events that might influence PK include, but may not be limited to the following:

- Adverse events, diarrhea etc. (these instances will be discussed on a case-by case basis)

- Vomiting after administration following oral dosing (these instances will be discussed in alignment with applicable regulatory guidelines on a case-by-case basis)
- Sample processing errors that may lead to inaccurate bioanalytical results
- Inaccurate dosing or dosing errors (e.g., dose administration delayed, dose change or missed doses)
- Pre-dose or trough sample collected after the actual dosing
- Non-compliance with food and drink requirements (e.g., non-fasted, incomplete meal consumption, caffeine intake)
- Concomitant medication, vitamins, dietary or herbal supplements

Should one or more of these events be available at the Data Review Meeting, its implication for PK evaluation will be discussed and agreed amongst relevant study team members (e.g., Sponsor Clinical Pharmacology/Biostatistics/Clinical Pharmacokinetics **C** [REDACTED] team representative). Appropriate action will be taken such as flagging individual values to be excluded from analysis.

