16.1.4 General Specifications for PK Concentration and PK Parameter Data

Predose samples that occur before the first drug administration will be assigned a time of 0 hours, as if the sample had been taken simultaneously with the study intervention administration. Same applies to the pre-dose sample after multiple doses.

Predose or trough samples which have been taken after the subsequent dosing will be reported as a protocol deviation. The resulting concentrations will be included in concentration listings but excluded from descriptive statistics of concentrations and from PK parameter estimation.

Values BLQ will be taken as zero for summary statistics of PK concentration data, PK parameter estimation (e.g., AUC) and for graphical presentations.

Missing concentrations (e.g., no sample, insufficient sample volume for analysis, no result or result not valid) will be reported generally as “N.R.”. A participant who withdraws prior to the last planned observation will be included in the analyses up to the time of discontinuation if still included in the PK analysis set.

If samples are collected outside of 10% of the PK sampling time windows defined in the CSP in Section 8.4, these will be included in the PK parameter estimation (NCA) but will be excluded from the concentration summary and mean/median concentration plots.

PK concentrations which are erroneous due to a sampling processing or analytical error (as documented in the bioanalytical report) may be excluded from the PK analysis if agreed by the Sponsor. In this case the rationale for exclusion will be provided in the CSR. Any other PK concentrations that appear implausible to the Clinical Pharmacologist/Clinical PK/PD Scientist will not be excluded from the analysis. Any implausible data will be documented in the CSR.

If important protocol deviations occurred likely to affect the PK profile of participants as specified in Section 10.2.1, the impacted concentrations and PK parameters will be excluded from summary statistics and further statistical evaluation.

Any PK concentrations or PK parameters excluded from summary statistics will be included in participants listings and flagged; a reason for exclusion will be detailed in the CSR (e.g., a footnote or a table of exclusions). Any flags will be included in the study specific CDISC data sets.

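### PK Analysis Set membership hangs on events up to Day 26, although the last evobrutinib sample is on Day 20, and the SAP has two different rules for participants who took a prohibited medicine

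*Protocol*

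**What the plan says.** Protocol 9.3 defines the PK Analysis Set, and SAP 8.1 repeats it. Members are those "Who have completed the study without any relevant protocol deviations and factors likely to affect the comparability of PK results", with adequate compliance and with values for the primary endpoints. A further sentence reads: "If participants received prohibited concomitant therapy or medicines, as specified in Section 6.8, they will be excluded from the PK population". All PK analyses use this set.

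Protocol 4.4 says what completion means: "A participant has completed the study if he/she has completed all study parts, including the Safety Follow-Up assessment". The synopsis places that assessment on Day 26.

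The Schedule of Activities (Protocol 1.3) gives the evobrutinib and metabolite sampling as "Sampling Days 1/2 and 19/20: Predose and 0.25, 0.5, 1, 1.5, 2, 2.5, 3, 4, 6, 8, 12, 16 and 24 hours postdose". The last sample is therefore on Day 20.

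Protocol 6.8.3 bans prescription and over-the-counter products, including vitamins, minerals and supplements, for a set time "prior to the first administration of study intervention, during the study, and until the Safety Follow-Up assessment".

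SAP 10.2.1 lists, among events that might influence PK, "Concomitant medication, vitamins, dietary or herbal supplements". For any such event, "its implication for PK evaluation will be discussed and agreed amongst relevant study team members" at the Data Review Meeting. SAP 16.1.4 adds that where an important deviation is likely to affect the PK profile, "the impacted concentrations and PK parameters will be excluded from summary statistics and further statistical evaluation".

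**The concern.** The primary result is two Day 19/Day 1 ratios, for AUC0-∞ and Cmax, from 18 planned participants who each serve as their own control. Once the 24-hour sample after the Day 19 dose is drawn, nothing later can alter either profile. Yet two membership criteria, study completion and absence of prohibited medicines, stay open until Day 26, and almost all of the intervening time is outpatient. Compliance has the same weakness: home carbamazepine intake starts on the evening of Day 20 and, under Protocol 6.4, is checked only at the Safety Follow-Up.

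Two things are at stake. Complete pairs may be discarded for reasons that cannot have affected them, which costs precision. And for medicines the plan holds two rules, so two analysts working from the same data could arrive at different PK sets. In an open-label study that choice would be made at data review, with the concentrations and dosing history to hand.

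**Working it through.** **Timeline.** Each profile has 1 predose and 13 postdose samples, so 14. The last is 24 hours after the Day 19 morning dose, on Day 20. The Safety Follow-Up is on Day 26, and 26 − 20 = 6 days.

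**The rules applied to the same participant (both profiles complete):**

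| Event | Protocol 9.3 / SAP 8.1 | SAP 10.2.1 / 16.1.4 |
|---|---|---|
| No Day 26 visit | Outside the set, because completion under Protocol 4.4 is not met | Membership not addressed |
| Vitamin first taken on Day 22 | Whole participant excluded; no condition on timing or relevance | Goes to the Data Review Meeting; under 16.1.4 no evobrutinib value is affected, so none is removed |
| Paracetamol given for wellbeing under Protocol 7.2 | Unclear: the definition points to Section 6.8, and 6.8.2 lists only ibuprofen and emergency medicines | Goes to the Data Review Meeting |

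**Cost in precision.** The justification of the 18 planned participants (Protocol 9.2) is redacted, so that figure cannot be reproduced. The planned model, with treatment fixed and subject random, reduces to a paired analysis when every member of the set has both days. The half-width of the 90% interval on the log scale is then

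h(n) = t(0.95, n−1) × s_w × √(2/n), with s_w = √ln(1 + CV²).

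The ratio h(n)/h(18) does not depend on the CV:

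| n | t × √(2/n) | Relative to n = 18 | Increase |
|---|---|---|---|
| 18 | 0.5799 | 1 | – |
| 17 | 0.5988 | 1.0327 | 3.3% |
| 16 | 0.6198 | 1.0689 | 6.9% |
| 15 | 0.6431 | 1.1091 | 10.9% |

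The within-subject CVs are redacted, so the next table uses assumed values. It shows exp(h), the factor by which the point estimate is multiplied and divided to get the limits:

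| Assumed CV | n = 18 | n = 17 | n = 16 | n = 15 |
|---|---|---|---|---|
| 20% | 1.122 | 1.126 | 1.131 | 1.136 |
| 30% | 1.186 | 1.192 | 1.200 | 1.208 |
| 40% | 1.250 | 1.259 | 1.270 | 1.281 |

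**Chance of a loss.** The visible text gives no rate. If each of 18 participants independently had probability p of a disqualifying event between the last sample and Day 26, the chance of losing at least one pair is 1 − (1 − p)^18. For assumed p of 2%, 5% and 10% this is 0.31, 0.60 and 0.85.

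**Evaluability (minor).** Requiring values for the primary endpoints is most naturally read as requiring both. A participant whose AUC0-∞ cannot be derived would then lose a valid Cmax as well. This should be rare, because SAP 16.1.5.1 flags poorly estimated AUC0-∞ values but keeps them.

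**The case against.** The best case for the plan has four parts.

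1. **Withdrawals.** SAP 16.1.4 keeps a withdrawn participant's data up to discontinuation if that participant is still in the PK set, which suggests that withdrawal does not automatically end membership. SAP 9.4 keeps such data without that condition. Protocol 7.1 and 7.2 also ask for the Safety Follow-Up visit after discontinuation, so a missed visit should be infrequent. The infrequency stands. The rest does not settle the matter: the 16.1.4 sentence defers to the set definition, and 9.4 does not amend it.

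2. **Two tiers for medicines.** One could read prohibited medicines as leading to exclusion and other medicines as going to review; SAP 10.2.2 does distinguish participant exclusion from exclusion of single concentrations. But neither document states that split, and SAP 10.2.1 names vitamins and supplements, which Protocol 6.8.3 prohibits. It is fair that 10.2.1 leaves the outcome open. That is a reason to settle it, not a reconciliation.

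3. **Redaction.** A hidden endpoint may need the later visit, and the hidden sample-size section may already allow for dropouts. Both are possible. The first is met by limiting the change to evobrutinib and its metabolite. The second would not make it useful to discard complete pairs.

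4. **Size.** The analysis is descriptive, the effect on the interval is small, and excluded profiles stay visible because individual PK listings use the Safety Analysis Set and reasons for exclusion are listed. All true, and it limits the importance of the point. The excluded pairs would still be missing from the primary ratios.

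**Conclusion.** The concern holds. As written, participants with two complete evobrutinib profiles leave the primary analysis because of a missed Day 26 visit or a medicine taken after the last sample. For medicines, Protocol 9.3 and SAP 8.1 also conflict with SAP 10.2.1 and 16.1.4.

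The precision cost is modest: a 3.3% wider log-scale interval for one lost pair and 10.9% for three. At an assumed CV of 30%, three lost pairs move the interval factor from 1.186 to 1.208. The percentages rest only on 18 planned pairs and the paired form of the model; the factors also rest on assumed CVs. How many pairs are at risk is unknown, and no bias has been shown. The ambiguity over who belongs in the set matters at least as much as the lost precision. The point should be fixed, and can be at little cost.

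**What to change.** Before database lock, for the evobrutinib and metabolite analyses only:

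- Replace study completion as a membership criterion with receipt of both evobrutinib doses and completion of the Day 1/2 and Day 19/20 PK sampling.
- Limit the deviation, compliance and prohibited-medicine exclusions to events up to the last Day 20 sample that could affect those profiles.
- Reconcile the categorical medicine exclusion in Protocol 9.3 and SAP 8.1 with the case-by-case handling in SAP 10.2.1 and 16.1.4, so that one rule governs. State how the set treats a participant given a medicine under the Protocol 7.2 allowance, which Section 6.8 does not list; those protocol passages must be reconciled.
- As a minor addition, judge evaluability parameter by parameter, so that a non-derivable AUC0-∞ does not remove a valid Cmax.

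The cost is wording in SAP 8.1 with cross-references to 10.2.1 and 16.1.4, plus matching text in Protocol 9.3 or an entry in SAP section 7. No new data are needed. N may then differ between parameters, and between these analytes and any redacted PK analyses, so each table must show its N.

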9.4 Imputation of Missing Data

In this Phase I PK study, missing observations will be assumed to be missing completely at random (MCAR). No action will be taken to handle missing data. A participant who withdraws prior to the last planned observation in a study period will be included in the analyses up to the time of discontinuation.

10 Study Participants

The subsections in this section include specifications for reporting participant disposition and study intervention/study discontinuations. Additionally, procedures for reporting protocol deviations are provided.

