16.1 Pharmacokinetics

PK evaluation will be performed by Nuvisan GmbH.

All statistical analyses and descriptive summaries of PK data will be performed on the PK Analysis Set.

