16.1.3 Statistical Analysis of PK Parameter Data

Analysis of Primary Endpoints

The effect of co-administration of carbamazepine on evobrutinib exposure will be assessed. A general linear model with a fixed effect for TREATMENT and a random effect for SUBJECT will be applied to the log-transformed PK parameters C_{max} and $AUC_{0-\infty}$ based on the PK analysis set.

Treatment differences on the log scale of evobrutinib with carbamazepine versus evobrutinib alone (Day 19 versus Day 1) will be estimated for the C_{max} and $AUC_{0-\infty}$ together with their 90% CIs. Point estimates and CIs will be back transformed to the original scale for presentation.

Analysis of Secondary Endpoints

The same analysis model as described for the primary endpoints will be provided for the secondary endpoint AUC_{0-tlast} of evobrutinib and C_{max}, AUC_{0-tlast} and AUC_{0-∞} of the evobrutinib metabolite MSC2729909A in plasma.

CCI

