The parameters C_{max} and t_{max} will be obtained directly from the concentration-time profiles. If C_{max} occurs at more than one timepoint, t_{max} will be assigned to the first occurrence of C_{max} .

The following PK parameters will be calculated for diagnostic purposes and listed, but will not be summarized:

- First (λ_z low) and last (λ_z up) time point of the time interval of the log-linear regression to determine λ_z .
- Number of data points ($N\lambda$) included in the log-linear regression analysis to determine λ_z .
- Goodness of fit statistic (adjusted R^2) for calculation of λ_z .
- AUC from time t_{last} extrapolated to infinity given as percentage of $AUC_{0-\infty}$. ($AUC_{extra\%}$)
- Span ratio of interval over which $t_{1/2}$ was estimated/ $t_{1/2}$

The regression analysis should contain data from at least 3 different time points in the terminal phase consistent with the assessment of a straight line on the log-transformed scale. Phoenix WinNonlin “best fit” methodology will be used as standard. If warranted, further adjustment may be made by the pharmacokineticist, after agreement with the Sponsor. The last quantifiable concentration $> LLOQ$ should always be included in the regression analysis, while the concentration at t_{max} and any concentrations BLQ which occur after the last quantifiable data point $> LLOQ$ should not be used.

If $AUC_{extra\%} > 20\%$ and/or the coefficient of correlation (R^2 adj) of λ_z is < 0.8 and/or the observation period over which the regression line is estimated (span ratio) is less than 2-fold the resulting $t_{1/2}$, the rate constants and all derived parameters (e.g. $t_{1/2}$, $AUC_{0-\infty}$, CL/F , etc.) will be listed, flagged and included in the parameter outputs. Should more than 10% of subjects be flagged for AUC_{extra} and/or R^2 adj (for a particular analyte), a sensitivity analysis excluding flagged parameters may be performed after discussion with the Sponsor.

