16.1.6 Presentation of PK Concentration and PK Parameter Data

16.1.6.1 Listings and Tables

The following PK tables will be produced (PK Analysis Set):

- Descriptive statistics of concentrations by analyte, matrix, and study intervention
- Descriptive statistics of PK parameters by analyte, matrix, and study intervention

The following PK Listings will be produced (Safety Analysis Set):

- Individual concentrations, nominal time by participant, analyte, matrix, study intervention sorted in chronological order
- Individual PK parameters by participant, analyte, matrix, day sorted in chronological order
- PK Sampling date, actual time, nominal time, deviation from time, percentage time deviation by participant, analyte, matrix, and study intervention sorted in chronological order
- Phoenix WinNonlin NCA Core Output

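### Because the PK Analysis Set requires non-missing primary endpoints, a participant whose evobrutinib AUC0-inf cannot be derived also drops out of the Cmax, AUC0-tlast and metabolite analyses

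*Protocol*

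**What the plan says.** Protocol 9.3 and SAP 8.1 use the same criterion for the PK Analysis Set: "With evaluable PK data, i.e., nonmissing values for primary endpoints". Protocol 3 and SAP 5 name the primary endpoints as evobrutinib AUC0-inf and Cmax. The criterion does not say both endpoints or both days, but that is its natural reading for a Day 19 versus Day 1 comparison.

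The set governs everything downstream. Protocol 9.3: "All PK analyses will be based on this analysis set". SAP 16.1: "All statistical analyses and descriptive summaries of PK data will be performed on the PK Analysis Set". SAP 16.1.3 models each parameter separately ("A general linear model with a fixed effect for TREATMENT and a random effect for SUBJECT will be applied") and carries that model to evobrutinib AUC0-tlast and to metabolite Cmax, AUC0-tlast and AUC0-inf ("The same analysis model as described for the primary endpoints will be provided for the secondary endpoint").

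AUC0-inf needs a terminal slope. SAP 16.1.5.1: "The regression analysis should contain data from at least 3 different time points in the terminal phase". The sample at tmax and trailing values below quantification may not be used. The same section flags but keeps values with extrapolation above 20%, adjusted R² below 0.8 or a short span.

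Individual values stay visible in SAP 16.1.6.1: "The following PK Listings will be produced (Safety Analysis Set"). On missing data, SAP 9.4 says "missing observations will be assumed to be missing completely at random (MCAR").

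**The concern.** Cmax and AUC0-tlast need no terminal slope. Metabolite parameters do not need the parent's slope, except the metabolite-to-parent AUC0-inf ratio. Yet the most fragile parameter decides whether any of a participant's PK results enter a model or summary. This can happen to a fully compliant completer.

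The loss may also be informative. Protocol Appendix 7 lists carbamazepine as a strong CYP3A inducer. Lower concentrations and a shorter half-life leave fewer quantifiable post-peak samples on Day 19, so failure to derive AUC0-inf can depend on exposure, contrary to the MCAR assumption. If the most strongly induced participants were the ones lost, the Cmax and AUC0-tlast ratios would move towards no effect.

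The rule also fits poorly with the rest of the plan. SAP 16.1.2 reports non-missing n for each parameter, and SAP 16.1.4 removes affected parameters individually after protocol deviations. Neither provision covers an AUC0-inf that cannot be derived.

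**Working it through.** The plan gives no figure for this event. The sample-size rationale is redacted, so 18 cannot be reproduced. The checks below therefore use ranges.

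**Inputs from the documents.** Sampling at 0.25, 0.5, 1, 1.5, 2, 2.5, 3, 4, 6, 8, 12, 16 and 24 h (Protocol 1.3). Half-life about 2 h without inducer, and fed tmax median 1.5 h, range 0.5 to 3 h (Protocol 2.2). Planned n = 18 (Protocol 1.1). At least 3 terminal points (SAP 16.1.5.1).

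**Assumed.** LLOQ, size of the induction effect, all variability terms.

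**1. Counting usable points.** After tmax, concentration as a fraction of Day 1 Cmax is r × 2^(−(t − tmax)/h), where r is the Day 19/Day 1 Cmax ratio and h the half-life. Example with r = 0.3, h = 1 h, tmax = 3 h: at 4, 6, 8 and 12 h the values are 15%, 3.75%, 0.94% and 0.06%. That leaves 3 points if the LLOQ is 0.5% of Day 1 Cmax, 2 at 1% or 2%, and 1 at 5%. With tmax 1.5 h and the same r and h, 4 or 5 points remain.

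The full grid is tmax 1.5, 2, 2.5, 3 h × LLOQ 0.5, 1, 2, 5% × h 1, 1.5, 2 h × r 0.2, 0.3, 0.5, or 4 × 4 × 3 × 3 = 144 cells. Eighteen cells have fewer than 3 points. All 18 have tmax 2.5 or 3 h, and 17 have a half-life below 2 h. None has an LLOQ of 0.5%. At 1% only two fail, both with tmax 3 h and h = 1 h.

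**2. Chance of the event.** One-compartment simulation, 4,000 profiles per scenario, absorption rate constant with median 1.2 per h. The table shows the probability that Day 19 AUC0-inf is missing.

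| Day 1 Cmax/LLOQ | r 1, h 2 h | r 0.3, h 1.5 h | r 0.2, h 1 h | r 0.1, h 1 h |
|---|---|---|---|---|
| 10 | 0.6% | 15% | 46% | 90% |
| 20 | 0.1% | 2.8% | 7.8% | 44% |
| 50 | 0% | 0.2% | 0.3% | 3.2% |
| 100 | 0% | 0.1% | 0.1% | 0.6% |
| 500 | 0% | 0% | 0% | 0% |

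For r 0.2 and h 1 h at a ratio of 20, the expected loss is 18 × 0.0777 = 1.4 participants and P(at least one) = 1 − (1 − 0.0777)^18 = 0.77. At 50 the probability is 0.06.

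Typical tmax in this scenario is ln(1.2/0.693)/(1.2 − 0.693) = 1.1 h, so late peaks are uncommon. A participant with tmax near 3 h is at more risk than these averages show, as step 1 indicates.

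Among profiles with a slope, extrapolation above 20% is more common (58% at ratio 20, 13% at ratio 50, for r 0.2 and h 1 h), but the SAP keeps those values.

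**3. Bias if participants are lost.** For n = 18 normal log ratios, the two smallest have expected standardised values of −1.820 and −1.350. Dropping the lowest shifts the mean by 1.820/17 = 0.107 SD; dropping the lowest two shifts it by 3.170/16 = 0.198 SD. With SD 0.3:

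- One lost: exp(0.3 × 0.107) − 1 = 3.3%.
- Two lost: exp(0.3 × 0.198) − 1 = 6.1%.

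These assume the lowest ratios are always the ones lost. Multiplying the shift by the correlation between loss and log ratio gives 1.6% and 3.0% at 0.5, 1.0% and 1.8% at 0.3, and 0% at zero.

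**4. Precision.** The upper 90% limit divided by the ratio is exp(t(0.95, n−1) × √(2 ln(1 + CV²)/n)). With an assumed within-subject CV of 30% this is 1.186 at n = 18, 1.200 at 16 and 1.208 at 15.

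**The case against.** The strongest reply is that the event may never occur. Thirteen post-dose samples cover a half-life of about 2 h, and at the documented median fed tmax of 1.5 h no grid cell falls below 3 points. The 3 h maximum comes from a high-fat breakfast study (Protocol 2.2), whereas this trial uses a moderate-fat meal (Protocol 5.3.1). SAP 16.1.5.1 keeps poor extrapolations and lets the pharmacokineticist adjust the regression with Sponsor agreement. SAP 10.2.2 lists reasons for exclusion, so a reader would see any dropped participant. The analysis is descriptive, with no hypothesis tests, and a 3% shift moves a ratio of 0.30 only to 0.31.

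All of this stands as to likelihood and size. It does not remove the rule: no text keeps Cmax or AUC0-tlast in the analysis when AUC0-inf cannot be derived.

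A reader might infer that the plan will bias the interaction towards no effect. The documents do not support that. They give no LLOQ and no predicted effect on evobrutinib; the Appendix 7 threshold of an 80% AUC decrease is an inducer class definition. On the grid, late tmax is necessary for loss, and nothing in the documents ties late tmax to a low Cmax ratio. A reader might also infer that measured data are thrown away. They are left out of models and summaries but remain in the listings.

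**Conclusion.** The point holds as a minor defect in the analysis-set definition. On the natural reading, one non-estimable evobrutinib slope removes a valid participant from the primary Cmax model and from secondary models that do not depend on it. That conclusion needs no assumption about the assay.

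Frequency and effect do rest on assumptions. The risk is material only if Day 1 Cmax is a low multiple of the LLOQ (about 20 or less under a strong effect), and negligible well above about 50. If 1 or 2 of 18 were lost, bias ranges from 0% to a ceiling of about 3% or 6% at SD 0.3 (2% to 8% across SD 0.2 to 0.4). The ceiling is a worst case, not an expected value. Loss of precision is slight.

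**What to change.** In Protocol 9.3 and SAP 8.1, replace the criterion with: *at least one evaluable primary PK parameter (AUC0-inf or Cmax) of evobrutinib*. Add three statements.

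- Each PK parameter is analysed in all PK-set participants for whom it is available. A non-derivable AUC0-inf then affects only what depends on it: AUC0-inf itself, CL/F, Vz/F, half-life and the metabolite-to-parent AUC0-inf ratio.
- Whether a participant with a parameter on only one day stays in the random-subject model for that parameter. The present text does not settle this.
- Where any AUC0-inf is not derivable, the already planned AUC0-tlast ratio in all participants is shown beside the AUC0-inf ratio. It complements AUC0-inf rather than replacing it, since it stops at the last quantifiable sample.

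The cost is wording in two documents, and n may differ between parameters in the tables. Settling it before database lock avoids a choice made with the data in view at the data review meeting.
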